In contradistinction, the studies by Worda et al⁸ and Connor et al.^{16-21,26,31} have examined topical eyelid androgen application with generally favorable effects on tear film parameters and also a good safety profile. However, the eyelid application studies were not consistent in the subject type (e.g., both males and females were not uniformly enrolled), the androgen status and serum levels were not assessed prior to, or following androgen application and the studies were only published as peer-reviewed abstracts and mostly were done in one laboratory. This prospective randomized, controlled double masked study aims to evaluate the efficacy and safety of topical transdermal application to the eyelids of low dosage androgen in a population of patients with evaporative dry eye associated with meibomian gland dystrophy and aqueous tear deficient dry eye.

Methods

Study objective

To evaluate the safety and efficacy of an FDA-approved androgen nasal supplement (Natesto, Acerus Pharmaceuticals Corporation, 4.5% gel concentration) in males and females with dry eye of either aqueous tear deficiency or evaporative subtype.

Clinical hypothesis

- Natesto applied to upper and lower eyelid skin is more effective than placebo as measured by fluorescein tear breakup time (TBUT) and mean scores for meibomian secretion quality at 4 weeks and overall ocular comfort at 8 weeks.
- Natesto has an acceptable safety profile in ocular structures and general systemic system.

Statistical Hypotheses:

H₀: There is no difference in change from baseline to week four for either fluorescein breakup time (TBUT) or meibomian secretion score (0 - 24 scale) between the test and placebo-treated sample.

 H_A : There is a difference in the change from baseline to week four for either fluorescein breakup time (TBUT) or meibomian secretion score (0 – 24 scale) between the test and placebo-treated sample

Overall study design

Structure

We propose a randomized controlled trial (RCT) of one month duration dosing BID with

an FDA-approved androgen nasal supplement (Natesto, Acerus Pharmaceuticals

Corporation, 4.5% gel concentration) in males and females with dry eye of either aqueous tear deficiency or evaporative subtype.

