- In this present investigation the principal outcome measures, fluorescein TBUT (using 2.0 microliters of 1.0% sodium fluorescein) and the system for meibomian gland secretion (0-24 scale) are recommended by the MGD workshop and DEWS II diagnostic committees.⁴ Table 2 shows the sample size estimation with two arm parallel design, comparing the change from baseline in FTBUT in each arm with a two sample t-test continuous data, clinically meaningful change of 2.5 seconds with Standard Deviation (SD) following treatment of 2.5 seconds. The results are as follow:
- 2-Sample t Test
- Testing mean $1 = \text{mean } 2 \text{ (versus } \neq \text{)}$
- Calculating power for mean 1 = mean 2 + difference
- $\alpha = 0.05$
- Assumed standard deviation = 2.5

Table 2: Sample size estimation

_	Difference	Sample Size	Target Power	Actual Power
	2.0	26	0.8	0.807487
	2.5	17	0.8	0.807037
	3.0	12	0.8	0.802079
	3.5	10	0.8	0.841306

4.0

0.8

0.844793

- 2.
- 3. With the actual power of 0.807, total of 34 subjects with seventeen (17) subjects per arm will be recruited for this study.

8

Randomization method

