Appendix III: Dry Eye Classification Criteria and Appendix V: Staging the Severity of MGD-Related Ocular Surface Disease

17. General statistical methods and types of analyses

- Comparisons, ANOVA, meibomian secretion scores, meibomian gland dropouts, OSDI
- The primary visit is week 4 and primary efficacy variables are the FTBUT and quality of meibomian secretions
- A two-sided test with p-value less than or equal to 0.05 will be considered as statistically significant.
- 18. Comparisons between pairs of treatment groups will be done with Cochran-Mantel Haenszel (CMH) tests, stratified by the ocular discomfort strata. Within Strata comparisons will be done with Wilcoxon rank-sum tests for both ordinal and continuous variables. For nominal variables, within strata comparisons will be done with Pearson's chi-square or Fisher's exact tests.
- 19. Exploratory pharmacokinetics data analysis
- Summary statistics of testosterone, dihydrosterosterone, and 3-alphaandrostanediol glucuronide serum concentrations will be calculated. The relationships between treatment time and gender will be examined.

Confidentiality

The identity of the subjects will be treated as confidential. The results of the study, including any other data, may be published for scientific purposes but will not reveal the name of the subject or include any identifiable references to the subject. Although

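### The power of 0.807 covers FTBUT alone, while the efficacy claim is stated once with 'and' and once with 'either', so no single success rule has been powered

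*Combined protocol and SAP*

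**What the plan says.** - **Sample size estimation.** FTBUT and the 0 to 24 secretion score are both called principal outcomes. The calculation is described as "comparing the change from baseline in FTBUT in each arm with a two sample t-test continuous data", with a "clinically meaningful change of 2.5 seconds with Standard Deviation (SD) following treatment of 2.5 seconds". The section ends: "With the actual power of 0.807, total of 34 subjects with seventeen (17) subjects per arm will be recruited for this study". No effect, SD or power is given for the secretion score or for comfort.
- **Clinical hypothesis.** The gel is to beat placebo on "fluorescein tear breakup time (TBUT) and mean scores for meibomian secretion quality at 4 weeks and overall ocular comfort at 8 weeks".
- **Statistical Hypotheses.** The alternative reads: "There is a difference in the change from baseline to week four for either fluorescein breakup time (TBUT) or meibomian secretion score". Comfort does not appear.
- **Evaluation criteria.** FTBUT and secretion grade are primary. The symptom questionnaires are secondary.
- **General statistical methods and types of analyses.** Week 4 is the primary visit, with the same two primaries. The only significance rule is: "A two-sided test with p-value less than or equal to 0.05 will be considered as statistically significant". Nothing says whether one or both primaries must reach it, and no multiplicity adjustment is given.

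**The concern.** A reader will take 0.807 as the trial's chance of success. Success has two definitions, and the figure fits neither. If every named measure must improve, success is harder than a significant FTBUT result. If either primary suffices, success is easier, but two tests at 0.05 carry more than a 5% false-positive risk.

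The two definitions also conflict on the same data. If one primary is significant and the other is not, the statistical null is rejected while the clinical hypothesis is unsupported. With no rule fixed beforehand, which reading governs the conclusion could be settled after the results are known.

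**Working it through.** **1. Reproduce the plan's figure.** Inputs from Sample size estimation: n = 17 per arm, difference 2.5 s, SD 2.5 s, two-sided alpha 0.05.

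- Standardised effect = 2.5 / 2.5 = 1.0
- Noncentrality = 2.5 / (2.5 × √(2/17)) = 2.915, with df = 2 × 17 − 2 = 32
- Noncentral t power = 0.8070, against 0.807037 in Table 2

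The other rows of Table 2 also reproduce (0.8075, 0.8021, 0.8413, 0.8448, taking n = 8 for the last row, whose n is lost in the text). The arithmetic is right, and it is FTBUT arithmetic.

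**2. 'And' rule: the ceiling.** P(both significant) ≤ P(FTBUT significant) = 0.807. This needs nothing beyond the plan's own FTBUT assumptions. Adding comfort cannot raise it.

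**3. 'And' rule: illustration.** Going below the ceiling requires an effect for secretion and a correlation between endpoints, and the documents give neither. Assume a one-SD secretion effect.

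- Independent endpoints, both significant: 0.807² = 0.651
- Independent endpoints, at least one significant: 1 − (1 − 0.807)² = 0.963
- Correlated endpoints: simulation at 17 per arm, 100,000 trials per setting, each endpoint tested by a two-sided 0.05 t-test

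| Correlation | Both significant | At least one | Exactly one |
|---|---|---|---|
| 0 | 0.65 | 0.96 | 0.31 |
| 0.3 | 0.68 | 0.94 | 0.26 |
| 0.5 | 0.69 | 0.92 | 0.22 |
| 0.7 | 0.72 | 0.89 | 0.17 |

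The last column is the third minus the second, taken before rounding.

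The result depends heavily on the assumed secretion effect. At 0.8 SD, power for both is about 0.50 to 0.58. At 1.2 SD it is about 0.75 to 0.78. At perfect correlation with equal effects it reaches 0.807.

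**4. 'Either' rule.** Power is at least 0.807, because a significant FTBUT result is enough. If neither endpoint has an effect:

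P(at least one false positive) = 0.05 + 0.05 − P(both)

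- Correlation 0: 0.10 − 0.0025 = 0.0975
- Correlation 0.5: about 0.09
- Correlation 0.7: about 0.085

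**5. Cost of an alpha split.** Repeating step 1 at alpha 0.025 gives FTBUT power of 0.712 with 17 per arm.

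**The case against.** The strongest reply is that the only formally stated test is the 'either' alternative, under which power does not fall. The clinical hypothesis can be read as a list of measures and not as a requirement that all succeed, and no section says all three must be significant. Comfort is neither a primary endpoint nor part of the formal alternative. The sizing paragraph openly says it concerns FTBUT, so 0.807 is not hidden or miscalculated.

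Most of this stands. A reader might infer that the trial really has power somewhere between 0.53 and 0.72 for its claim. The documents do not support that. The low end takes three independent endpoints (0.807³ = 0.526) and the high end takes two endpoints at correlation 0.7. Both rest on assumed one-SD effects, and the range is not a bound. Nor is a split result likely: at 17 to 31% in the illustration it is material, but it is the minority outcome.

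The reply does not remove the contradiction between the two hypotheses or the missing success rule. Taking 'either' as the rule also leaves two unadjusted tests at 0.05.

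**Conclusion.** The point holds as an inconsistency in the hypotheses and in the scope of the power statement. It is not an arithmetic error.

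- 0.807 is correct for FTBUT under the t-test assumptions and is the power of neither stated rule.
- Under 'and', joint power is unknown and at most 0.807. The 0.65 to 0.72 for two primaries is an illustration, conditional on a one-SD secretion effect and correlation from 0 to 0.7.
- Under 'either', power is at least 0.807, with a false-positive chance of about 0.085 to 0.0975 over the same correlations.

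This should be corrected before unmasking. It does not show that the trial is too small for the test it was sized on.

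**What to change.** 1. **Sample size estimation.** State that 0.807 is the power for FTBUT alone under the t-test assumptions, and that power for benefit on both primaries was not calculated and is no higher than this. Do not enter 0.65 to 0.72 as an established figure, since no secretion effect supports it.
2. **Clinical hypothesis and Statistical Hypotheses.** Before unmasking, replace the two versions with one decision rule and repeat it in the general statistical methods section. The option that matches the sizing is to test FTBUT at week 4 first at two-sided 0.05, test secretion score at week 4 at 0.05 only if FTBUT is significant, and treat comfort as a separate secondary claim. This holds the false-positive chance across the two primaries at 0.05. The 0.807 then belongs to the deciding test, provided that test is the t-test used for sizing; the analysis section names ANOVA, CMH and Wilcoxon tests, so it should say which applies.

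The cost is a few sentences, with no added subjects or procedures. The drawback is that no formal secretion claim is possible if FTBUT fails. If the sponsor wants secretion to keep equal standing, it can require both primaries (joint power unknown, at most 0.807) or split alpha (FTBUT power 0.712 at 0.025). Either way, the protocol should state the power of the rule chosen.

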- Comparison of National eye Institute (NEI) to Ocular Staining Score (OSS) (DEWS II recommendation) staining scheme for efficiency
- 2. Repeatability of the above two staining schemes and meibomian gland secretion scores

Pharmacokinetic measures

• The patients will have blood samples (20 ml) drawn for the determination of total serum testosterone. Blood will be drawn at baseline and within two hours of dose application at Week 4 visit.

Safety measures

- Adverse events (treatment related and treatment unrelated)
- Visual acuity (BCVA ETDRS)
- Biomicroscopy
- Ophthalmoscopy exam
- IOP
- Male scalp hair evaluation
- Female hair evaluation (upper lip, chin, cheeks, scalp)

Subjects

Subjects will consist of a convenience sample of patients over 18 years old with signs and symptoms of dry eye disease (DED). Moderate to severe dry eye subjects who have either aqueous tear deficiency or evaporative dry eye related to meibomian gland

dysfunction will be recruited. The diagnosis of DED is made according to the DEWS II diagnostic criteria based on:

- 1. DE symptomatology: OSDI score \geq 13 and Modified Schein score \geq 7.5
- 2. Plus one of the following:
 - a. NIBUT < 10 seconds or fluorescein breakup time ≤ 6.0 seconds or
 - b. Osmolarity \geq 308 mosm/L in either eye or intraocular difference > 8 mosm/L or
 - Ocular surface staining (SICCA scale) > 5 corneal spots, > 9 conjunctival spots
 - d. Conjunctival-corneal epithelial damage (fluorescein, rose bengal, or lissamine green staining score >3 points).
- 3. Subtype Tests: severity according to the DEWS II Dx report;⁴ page 556
 - a. Aqueous tear deficiency: non-invasive meniscus height (TMH) ≤ 0.2 mm
 - b. Evaporative: only moderate to severe included:
 - Moderate: 1) orifice plugging, 2) lid margin vascularity, 3) gland secretion grade 8 – 12 (central 8 glands, 0 – 3 scale each),
 4) expressibility grade 2
 - Severe: 1) lid margin dropout or displacement, 2) gland secretion score ≥ 13, 3) expressibility grade of 3

The subjects will be recruited from among students, staff, faculty and patients from Ketchum Health, the clinical facility at Marshall B. Ketchum University. Additionally, the study will be advertised on social media to maximize the recruitment pool, such as Facebook, Instagram, and Twitter. Subjects will be sex-, and age-matched as they are enrolled since these parameters affect dry eye parameters such as marginal changes and meibomian gland secretion. ⁴⁴

Sample size estimation

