Due to the relatively small sample size (n < 200) and the need to control and balance the influence of covariates, such as age and sex, we adopted the method of covariate adaptive randomization.⁴⁵ With two covariates of sex (2 levels: male, female) and age (2 levels: <50, >50) between study arms (treatment and control), a total of 4 block combinations is produced. After a participant has passed the screening and day 0 examinations, the first 10 participants will be assigned to one of the treatment groups within each block by simple randomization, according to a randomization scheme ([name] [name] will generate this). The next new participant is then sequentially assigned to a particular treatment group by considering the specific covariates and previous assignments of participants. For example, the first 10 participants assignment are broken down by covariates as in Table 3. Then the 11^{th} participant, who is male and >50 years old, needs to be assigned to a group (control vs. treatment). Based on the characteristics of the 11th participant, the method adds marginal totals of the corresponding covariate categories for each group and compares the totals. The participant is assigned to the group with the lower covariate total to minimize imbalance. In this example, the appropriate categories are male and > 50 years old, which results in a total of 6 (3 for male and 3 for >50) for the control group and a total of 5 (3 for male and 2 for >50) for the

treatment group. Because the sum of marginal totals is lower in treatment group

(5<6), the 11th participant is assigned to the treatment group.

Control group		Sex	Marginal total	
		Male	Female	
Age	<50	2	0	2
	>50	1	2	3
Marginal total		3	2	5

Table 3. Procedure of randomization

Treatment group		Sex	Marginal total	
		Male	Female	
Age	<50	1	2	3
	>50	2	0	2
Marginal total		3	2	5

Every participant is assigned a number from 001 to 100 and recorded with the specific number during the whole study until de-identified at the end of the study.

Masking

- 1. The participants will be masked from the assignment of the treatment group.
- An unmasked research assistant will recruit and schedule subjects and administer the questionnaires and exclude subjects based on the above-mentioned inclusion and exclusion criteria.
- 3. Another unmasked research assistant will implement the randomization based on the above covariate adaptive randomization method.

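### Arms are balanced on sex and age group, but no efficacy analysis names either factor; if they predict the change score, the unadjusted test is conservative and gives up power that adjustment would recover almost free

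*Combined protocol and SAP*

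**What the plan says.** **Allocation.** The Randomization method section gives as a reason "the need to control and balance the influence of covariates, such as age and sex, we adopted the method of covariate adaptive randomization". The factors are defined as: "With two covariates of sex (2 levels: male, female) and age (2 levels: <50, >50) between study arms". The first 10 participants are assigned by simple randomization. From the 11th on, each goes to the arm with the smaller sum of marginal totals for that person's sex and age group.

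**Why these factors.** The Subjects section says participants are matched on sex and age "since these parameters affect dry eye parameters such as marginal changes and meibomian gland secretion". Secretion grade is one of the two primary measures. The other, fluorescein breakup time (FTBUT), is not named there.

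**Analysis.** The sample size rests on "comparing the change from baseline in FTBUT in each arm with a two sample t-test continuous data". The General statistical methods section lists ANOVA without model terms, and CMH tests stratified by ocular discomfort, which is not an allocation factor. It adds: "Within Strata comparisons will be done with Wilcoxon rank-sum tests for both ordinal and continuous variables". Significance is defined by: "A two-sided test with p-value less than or equal to 0.05 will be considered as statistically significant". Gender appears only in the exploratory pharmacokinetic analysis.

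**The concern.** Minimisation removes most of the chance imbalance in sex and age between the arms. If these factors predict the outcome, the treatment difference varies less from trial to trial than it would under simple randomization. An unadjusted test does not register this. It leaves the between-sex and between-age variation in its residual variance, so its standard error is too large.

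Confidence intervals would then be wider than necessary and the real significance level would fall below 5%. The trial would also not collect the full benefit of the balance it built in. With 34 subjects, a few points of power are worth having.

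**Working it through.** **Inputs from the documents.** Two-sided alpha 0.05; "clinically meaningful change of 2.5 seconds with Standard Deviation (SD) following treatment of 2.5 seconds"; "With the actual power of 0.807, total of 34 subjects with seventeen (17) subjects per arm will be recruited for this study"; and the allocation rule described above.

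**Assumptions.** R², the share of variance in the change score explained by sex and age group together, is not given, so a range is shown. Also assumed: normal outcomes, equal contributions from the two factors, half the subjects in each level of each factor, ties broken at random, and no dropout.

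**Step 1: reproduce the plan's figure.** SE = 2.5 × √(2/17) = 0.857. Noncentrality = 2.5/0.857 = 2.92 on 32 degrees of freedom. Power = 0.807, as in Table 2.

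**Step 2: what balance should do.** With perfect balance on both factors, the true SD of the treatment difference is 0.857 × √(1 − R²), while the unadjusted SE stays near 0.857.
- R² = 0.1: 0.857 × √0.9 = 0.813
- R² = 0.2: 0.857 × √0.8 = 0.767
- R² = 0.3: 0.857 × √0.7 = 0.717

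**Step 3: simulate the actual rule.** There were 12,000 trials per setting. Monte Carlo error is about 0.002 for type I error and 0.004 for power. The adjusted analysis is a linear model with treatment, sex and age group.

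| R² | Unadjusted SE | True SD | Type I, t-test | Type I, Wilcoxon | Power, t-test | Type I, adjusted | Power, adjusted |
|---|---|---|---|---|---|---|---|
| 0 | 0.857 | 0.849 | 0.050 | 0.047 | 0.807 | 0.049 | 0.804 |
| 0.1 | 0.860 | 0.817 | 0.039 | 0.039 | 0.821 | 0.051 | 0.847 |
| 0.2 | 0.859 | 0.775 | 0.031 | 0.029 | 0.831 | 0.051 | 0.886 |
| 0.3 | 0.862 | 0.728 | 0.024 | 0.023 | 0.842 | 0.052 | 0.919 |
| 0.5 | 0.865 | 0.620 | 0.009 | 0.009 | 0.871 | 0.050 | 0.977 |

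The simulated SDs sit just above those of step 2, because the first 10 assignments are not balanced. The unadjusted SE is too large by 0.860/0.817 = 1.05, 0.859/0.775 = 1.11 and 0.862/0.728 = 1.18 at R² of 0.1, 0.2 and 0.3. With 75% of one sex the results are almost the same.

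**Step 4: small R².** In a separate run of 6,000 trials per setting, R² = 0.02 gave type I error 0.045 and power 0.802 unadjusted against 0.808 adjusted. R² = 0.05 gave 0.046, and 0.811 against 0.821.

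**Step 5: isolate the cause.** Under simple randomization the unadjusted t-test keeps type I error between 0.048 and 0.053 at every R². The conservatism therefore comes from pairing minimisation with an unadjusted test.

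**Step 6: would stratifying the rank test do instead?** Four sex-by-age cells average 34/4 = 8.5 subjects, about four per arm. A Wilcoxon stratified by these cells had power 0.736 against 0.786 unstratified at R² = 0, 0.741 against 0.782 at 0.05, 0.785 against 0.800 at 0.1, and 0.821 against 0.806 at 0.2. A second run agreed: 0.745 against 0.788 at R² = 0, and 0.781 against 0.797 at 0.1. If the discomfort strata are kept as well (two levels assumed), cells average 34/8 = 4.25 subjects and power falls to 0.63–0.72 over R² of 0 to 0.2.

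**The case against.** The strongest reply is that the effect depends wholly on R², which the documents do not give. The protocol asserts an influence on lid-margin changes and meibomian secretion, which reads as an association with levels. The endpoint is change from baseline, where a stable difference in level cancels. FTBUT, the only powered endpoint, is not mentioned. The background does report a better response to testosterone cream in women aged 40 to 60, but that looks like differential treatment response, and the age band straddles the cut at 50. **This stands.** It makes the point conditional and rules out a firm size for either primary.

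A second reply is that the direction is harmless. **This also stands.** A reader might infer that the stated 5% level and 0.807 power are not delivered, or that the sample size is wrong. The documents do not support that. Table 2's figure reproduces, type I error is at or below 5%, and at the planned 2.5 s difference unadjusted t-test power equals or exceeds the stated figure within simulation error.

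A third reply is that ANOVA is listed without terms, so the model is unspecified and sex and age are not actually excluded. **That is a fair reading.** It leaves the same gap: nothing commits the analysis to the allocation factors.

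**Conclusion.** The point holds in conditional form. The plan balances on two factors for the stated reason that they matter, then names neither in any efficacy analysis. If they explain 10% to 30% of the variance in the change score, the unadjusted test runs at about 4% to 2% instead of 5%. It then forgoes about 3 to 8 points of power against the adjusted model (0.847 − 0.821 = 0.026 at R² = 0.1; 0.919 − 0.842 = 0.077 at R² = 0.3). At R² of 0.05 or less the difference is about one point or less. At R² = 0 nothing is distorted.

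The missed opportunity is one of efficiency. It does not threaten validity and is no ground for enlarging the trial. A reader might also infer that every planned test should be stratified by sex and age; step 6 shows that for the rank test this loses power until R² is somewhere between 0.1 and 0.2. This is a nearly free improvement, held with moderate confidence because R² is assumed throughout.

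**What to change.** For each week-4 primary, pre-specify a linear model on change from baseline with treatment, sex and age group as terms, using the levels that drove assignment. State which level a participant aged exactly 50 belongs to, since the levels as written leave that age out. Report the unadjusted test as a sensitivity analysis. Do not stratify the Wilcoxon or CMH test by the sex-by-age cells.

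The cost is a sentence or two in the statistical methods section and two degrees of freedom (32 to 30). Both factors are already recorded at assignment. If they turn out to explain nothing, the loss is about 0.3 points of power (0.807 − 0.804). No extra subjects are needed. The choice should be made before unmasking, so that it cannot be made between two known results.

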The test formulation will be marketed Natesto gel, containing 5.5 mg testosterone per pump (17 β -Hydroxyandrost-4-en-3-one; inactive ingredients are castor oil, oleoyl polyoxylglycerides and colloidal silicone dioxide; Natesto package insert). The placebo is the exact same formulation without 17 β -Hydroxyandrost-4-en-3-one. The drug and placebo will be delivered to and dispensed by Caduceus Medical group in Yorba Linda for MBKU's study use.

Dosage regimen

One dose per eyelid of masked gel, which is one pump from the dispenser, represents 5.5 mg for each eyelid, will be applied on the surface of upper and lower eyelid skin each eye twice per day (separated by 8 hours) for a total daily dose of 22mg.

Duration

2-week screening period; 4-week masked treatment phase, 8-week washout phase.

Overall study duration 14 weeks

Visit schedule (see Table 4 and 5)

- Visit 1: Screening visit (Day -14)
- Visit 2: Baseline (Day 0) : the drug (placebo) is prescribed and dispensed.
 Instructions are given on how to properly apply the drug. Subjects are instructed to keep the container even if the drug is finished. All containers need to be checked in the following two visits (visit 3 & 4)
- Visit 2a: serum blood draw for baseline total testosterone level, hematocrit, lipid panel, PSA for men only at clinical laboratory

- Visit 3: Two-week visit: check the drug (placebo) to see if supplement needed.
 Empty containers need to be collected.
- Visit 4: Week 4: the drug (placebo) is discontinued. All dispensed containers need to be collected.
- Visit 4a: serum blood draw for treatment period total testosterone level at clinical laboratory (must be in AM, and must be within two hours of application)
- Visit 5: Week 8: 4-weeks washout phase follow up
- Visit 6: Week 12: 8-week washout phase follow up

Evaluation criteria

Efficacy measures

Primary

- Fluorescein tear breakup time (FTBUT)
- MGD secretion grade (0-24 scale)

Secondary:

- 1. Schein Questionnaire and Ocular Surface Disease Index (OSDI)
- Corneal and conjunctival staining as per the Oxford and National Eye Institute (NEI) schemes
- Tear Meniscus Height (TMH) utilizing Keratography 5M (K5M Oculus, Inc Arlington,WA)
- 4. Eyelid signs grading of orifice metaplasia, vascularity, plugged orifice, lid margin irregularity, ridging between orifices, and antero-posterior orifice displacement
- 5. Meiboscore utilizing K5M
- 6. Schirmer I test without anesthetic

Exploratory:

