- 4. The principal investigator is masked from tests and placebo formulation during the follow up dry eye evaluations on subjects.
- 5. All masked information will only be opened at the end of the study or unless an adverse event (AE) requires unmasking to determine whether the AE was due to the treatment medication.

Study Sites

 Southern California College of Optometry at Main Campus ([name]). Main site for dry eye examination

Inclusion & Exclusion Criteria

Inclusion criteria

There are no restrictions for subject inclusion based on ethnicity, race, or occupation. All subjects meet the following criteria:

- 1. Male or female age over 18
- 2. Able and willing to follow study instructions.
- 3. Are able to provide written informed consent
- 4. Written authorization for use or release of health and research study information will be obtained
- Are willing to discontinue use of artificial tears and makeup on the study visit days
- 6. Able and willing to attend the clinical laboratory for morning blood draws to assay serum testosterone in addition PSA levels for men.
- 7. Patient must have a best corrected visual acuity of 20/40 or better in each eye
- 8. Patients must have normal lid position and closure

- Patients' willingness and ability to cooperate with the investigator and follow all instructions
- 10. A negative urine pregnancy test result for women of childbearing potential
- 11. Women of childbearing potential (from 18 to 50 years old) must have a history of bilateral tubal ligation or use contraceptives, implants, injectables, transdermal patch or IUD for birth control during the study. Patients taking oral contraceptives must not miss 2 or more doses in a one-month period. If these methods of birth control do not apply, women of childbearing potential must have a monogamous partner who has had a vasectomy at least 3 months before the screening visit. The date of the vasectomy and physician contact information must be documented in the source documents.
- 12. Subjects must have a meibomian gland secretion score of 8 or greater (0 24 scale).
- 13. Subject s must have at least 50% meibomian glands present in the upper eyelids.

Exclusion criteria

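### The assistant who recruits and schedules is unmasked although the role does not need the allocation, and anyone who knows earlier assignments can partly foresee later ones

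*Combined protocol and SAP*

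**What the plan says.** All references are to the combined protocol and SAP.

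- **Masking, item 2:** "An unmasked research assistant will recruit and schedule subjects and administer the questionnaires and exclude subjects". No reason is given for leaving this person unmasked.
- **Masking, item 3:** "Another unmasked research assistant will implement the randomization based on the above covariate adaptive randomization method". Recruiting and assigning are therefore two people's work.
- **Randomization method, timing:** "After a participant has passed the screening and day 0 examinations, the first 10 participants will be assigned" by simple randomization. This is read as the first 10 overall, because the worked example moves on to the 11th participant.
- **Randomization method, rule from subject 11:** "The participant is assigned to the group with the lower covariate total to minimize imbalance". The totals are marginal counts for the new subject's sex and age level. Nothing is said about equal totals. The age levels are below 50 and above 50, so a subject aged exactly 50 has no level.
- **Subjects:** "Subjects will consist of a convenience sample of patients over 18 years old".
- **Masking, item 4:** "The principal investigator is masked from tests and placebo formulation during the follow up dry eye evaluations on subjects".
- **Masking, item 5:** "All masked information will only be opened at the end of the study", or earlier if an adverse event requires it.

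**The concern.** The lower-total rule has three inputs: sex, age level and earlier assignments. A recruiter learns the first two in the ordinary course of the job. Being unmasked opens the third. A person with all three can often tell which arm the next subject will enter. In a convenience sample, that person can choose whom to approach and when to schedule them.

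If likely good responders were brought in when treatment was expected, the arms would differ at entry. Masked follow-up examinations would not remove that difference. With 34 subjects a few steered enrolments carry weight, and such selection is hard to detect or correct afterwards.

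**Working it through.** **1. The plan's own figures.** Sample size estimation gives 17 per arm, a 2.5 s difference, SD 2.5 s, two-sided alpha 0.05 and power 0.807037. The exact noncentral t calculation gives 0.80704, so the figure reproduces. N = 34 leaves 34 - 10 = 24 subjects under the lower-total rule.

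**2. Table 3 of the plan.** Marginal totals are: control male 3, female 2, <50 2, >50 3; treatment male 3, female 2, <50 3, >50 2. The worked example (male, >50) is 3 + 3 = 6 v 3 + 2 = 5, so treatment, as stated. For every profile that subject 11 could have:

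| Profile | Control | Treatment | Arm |
|---|---|---|---|
| Male <50 | 3+2 = 5 | 3+3 = 6 | Control |
| Male >50 | 3+3 = 6 | 3+2 = 5 | Treatment |
| Female <50 | 2+2 = 4 | 2+3 = 5 | Control |
| Female >50 | 2+3 = 5 | 2+2 = 4 | Treatment |

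All four are fixed before anyone is approached.

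**3. How much can be foreseen.** The rule was simulated for 34 subjects. Three inputs are not in the plan and are assumed:

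- Ties are broken 50:50.
- The main mix is 35% male and 50% over 50. The alternatives are 15% male with 70% over 50, and 50% male with 50% over 50.
- The number of subjects recruited but not yet assigned (pending) is varied, because no accrual rate is given.

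Every figure also assumes that the recruiter knows earlier assignments. With none pending, about 18.3 of 24 arms are fixed (5th-95th percentile 15-21) and about 5.7 are ties. Correct guesses are then (18.3 + 0.5 x 5.7)/24 = 0.88.

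| Pending, sex and age unknown | Correct, main mix | Correct, all mixes | Arms still fully fixed, main mix |
|---|---|---|---|
| 0 | 88% | 88% | 18.3 |
| 1 | 68-71% | 60-73% | 3.4 |
| 2 | 65-67% | 65-68% | 1.3 |
| 4 | 60-62% | 60-63% | 0.1 |

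Main-mix ranges run from a guess on current totals to the best guess averaged over the unknown pending profiles. If the pending subjects' sex, age and order are known, the main-mix figures for 1, 2 and 4 pending are 83%, 78% and 72%. A masked recruiter guesses at 50%.

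**4. What steering could do.** Suppose that whenever treatment is expected, the recruiter enrols someone whose outcome will be better by d = 0.3 or 0.5 SD. Both d and the behaviour are assumed, as a worst case. With p the proportion of correct guesses, and half the 24 guesses naming treatment, the net number of steered treated subjects is 12 x (2p - 1). For p = 0.683 this is 4.4. Bias is 2.5 s x d x (net steered / 17). For 5.1 steered and d = 0.5: 2.5 x 0.5 x 5.1/17 = 0.38 s. Type I error is for the two-sample t-test used in the sample size section. Main mix:

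| Pending, unknown | Net steered | Bias, d = 0.3 / 0.5 | Type I error, d = 0.3 / 0.5 |
|---|---|---|---|
| 1 | 4.4-5.1 | 0.19-0.23 / 0.32-0.38 s | 0.056-0.057 / 0.067-0.072 |
| 2 | 3.7-3.9 | 0.16-0.17 / 0.27-0.29 s | 0.054 / 0.061-0.063 |
| 4 | 2.5-2.9 | 0.11-0.13 / 0.18-0.21 s | 0.052 / 0.055 |
| 0 (upper bound) | 9.2 | about 0.4 / 0.7 s | about 0.074 / 0.117 |

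With d = 0 the simulated Type I error is 0.050.

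**The case against.** The strongest reply is that the premise is undocumented. No text says that the recruiter sees assignments. A second assistant assigns, and an outside medical group dispenses the gel and placebo. **This stands:** what is documented is an unneeded permission, not a leak. A reader might infer that the recruiter holds the running totals or that enrolment is biased; the documents support neither. Item 5 does not settle the matter, because it does not say that it binds staff named as unmasked.

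The route is also narrow. Assignment follows the screening (Day -14) and day 0 examinations, so pending subjects blur any forecast. Eligibility rests largely on measured thresholds, and discretionary exclusions belong to the investigator. Tear breakup time and gland scores are examination findings obtained at the screening visit and later. Questionnaires are not scored until the subject's data capture is complete. **All of this stands.** It leaves open whom to approach and when to schedule. A reader might also infer biased symptom scores from an unmasked assistant giving the questionnaires; no such claim is made here.

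The 88% figure is tempting but needs nobody pending. With 14 days from screening to day 0, one-at-a-time enrolment of subjects 11-34 would take 24 x 14 = 336 days, or 48 weeks. It is an upper bound only. Nor is every assignment from subject 11 determined: about a quarter are ties with no stated rule.

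Finally, the 0.3-0.5 SD advantage has no source in the plan, and the resulting effects are small. That is accepted. It limits the size of the point but is no reason to keep a permission that serves no stated purpose.

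**Conclusion.** The point holds in a limited form. The plan leaves the recruiting assistant unmasked without a stated reason, pairs this with a rule that has no random element outside ties, and states no step that hides earlier assignments from that assistant. Selection at approach or scheduling is possible, not shown.

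The size depends on assumed recruiter knowledge, 50:50 ties and an assumed sex and age mix. With one to four subjects of unknown profile pending, guesses are right about 60-73% of the time. Even under worst-case steering, the distortion is well below the planned effect. The missing tie rule (about 6 of 24 assignments) and the missing category for age 50 are gaps whatever the recruiter knows. The change is worth making because it closes the route at almost no cost, not because serious bias is likely.

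**What to change.** - **Masking, item 2:** state that the recruiting and questionnaire assistant is masked to all assignments and running totals.
- **Masking, item 3:** state that only the second assistant holds them.
- **Randomization method:** state that equal totals are broken at random, and define the age levels as <50 and >=50.

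This is protocol wording only. It needs no extra staff, because a separate assistant already assigns, and it changes neither the sample size nor the lower-total rule that gives sex and age balance. No further change to timing is needed, since the plan already assigns after the screening and day 0 examinations.
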